6.2. Appendix 2: Protocol Deviations

Major protocol deviations will be summarized.

In general, the following list of major protocol deviations may have the potential to impact participants' rights, safety or well-being, or the integrity and/or result of the clinical study. Participants with major protocol deviations will be identified prior to database lock and the participants with major protocol deviations will be summarized by category.

- Developed withdrawal criteria but not withdrawn
- Entered but did not satisfy criteria
- Received a disallowed concomitant treatment
- Received wrong treatment or incorrect dose
- Other

Protocol deviations that influence immunogenicity will be flagged in a listing.

In addition, major protocol deviations and eligibility violations will also be summarized by study intervention group. Protocol deviations for this study include, but are not limited to, the following (see also the Major Protocol Deviation Criteria Form for this study for more details):

- Failure to meet inclusion/exclusion criteria
- Use of a prohibited concomitant medication/vaccination
- Any other deviation that presents significant risk or safety concerns to the patient

6.3. Appendix 3: Prior and Concomitant Medications

The analysis of concomitant therapies will be done using the WHO drug coded terms.

Based on their start and stop date, concomitant therapies will be reported in each applicable phase.

If a concomitant therapy record misses components of its start and/or stop dates (time, day and/or month and/or year):

- In case of partial start or stop dates, the concomitant therapy records will be allocated to periods using the available partial information, without imputations. If, for example, only month and year are available, these will be compared to the month and the year of the periods, and the concomitant therapy record will be allocated to the period(s) where these date parts match. This rule may lead to assignment to multiple periods.
- In case of a completely missing start date, the concomitant therapy will be considered as having started before the trial.
- In case of a completely missing end date, the concomitant therapy will be considered as ongoing at the end of the trial.

There will be special attention to any systemic use of analgesics/antipyretics, started during 14 days following each vaccination (00:00 of day of vaccination + 14 days). Following ATC/DDD codes will be used for this: N02A (OPIOIDS) and N02B (OTHER ANALGESICS AND ANTIPYRETICS), M01A (ANTIINFLAMMATORY AND ANTIRHEUMATIC PRODUCTS, NON-STERIODS) and M01B (ANTIINFLAMMATORY/ANTIRHEUMATIC AGENTS IN COMBINATION). The classes will be added in a footnote in all related tables and listings. For the use of analgesics/antipyretics which are taken on the day of vaccination, an exception is made in case the time is before vaccination. In this case, the concomitant medication is also allocated to the Post-dose period.

6.4. Appendix 4: Toxicity Grading Scale for Vital Signs

Adapted from the Food and Drug Administration Guidance document “Toxicity Grading Scale for Healthy Adult and Adolescent Volunteers Enrolled in Preventive Vaccine Clinical Trials” (September 2007)

Vital Signs *	Mild (Grade 1)	Moderate (Grade 2)	Severe (Grade 3)	Potentially Life Threatening (Grade 4)
Fever (°C) ** (°F)**	38.0 - 38.4 100.4 - 101.1	38.5 - 38.9 101.2 - 102.0	39.0 - 40.0 102.1 - 104.0	> 40 > 104.0
Tachycardia - beats per minute	101 – 115	116 – 130	> 130	Hospitalization for arrhythmia [#]
Bradycardia - beats per minute***	50 – 54	45 – 49	< 45	Hospitalization for arrhythmia [#]
Hypertension (systolic) - mm Hg	141 – 150	151 – 160 [#]	> 160 [#]	Hospitalization for malignant hypertension [#]
Hypertension (diastolic) - mm Hg	91 – 95	96 – 100	> 100	Hospitalization for malignant hypertension [#]
Hypotension (systolic) – mm Hg	85 – 89	80 – 84	< 80	Hospitalization for hypotensive shock [#]
Respiratory Rate – breaths per minute	17 – 20	21 – 25	> 25	Intubation

* Participant should be at rest for all vital sign measurements.

** For oral temperature: no recent hot or cold beverages or smoking.

*** When resting heart rate is between 60 – 100 beats per minute. Use clinical judgment when characterizing bradycardia among some healthy participant populations, for example, conditioned athletes.

[#] Revised by the sponsor.

For the vital signs analysis in Section 5.6.2, only values will be used to assign abnormalities, no clinical interpretations will be used. Therefore, Grade 3 and 4 will be combined because Grade 4 always requires clinical interpretation.

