## **10.3.3. Severity Criteria**

All AEs and laboratory data will be coded for severity using a modified version of the FDA grading table, based on version of September 2007 ([US Dept Health 2007a](#)), included in [Appendix 5: Toxicity Grading Scale](#).

For AEs/MAAEs not identified in the grading table, the following guidelines will be applied:

Grade 1	Mild	Symptoms causing no or minimal interference with usual social and functional activities
Grade 2	Moderate	Symptoms causing greater than minimal interference with usual social and functional activities
Grade 3	Severe	Symptoms causing inability to perform usual social and functional activities and requires medical intervention
Grade 4	Potentially life-threatening	Symptoms causing inability to perform basic self-care functions OR medical or operative intervention indicated to prevent permanent impairment, persistent disability OR ER visit or hospitalization

The severity of solicited signs and symptoms will be graded in the eDiary by the participant based on the severity assessment provided in the eDiary and then verified by the investigator using the toxicity grading scale in [Appendix 5: Toxicity Grading Scale](#). (Note: severity of the measured events will be derived from the diameter [for erythema and swelling] and the temperature measurements [for fever]).

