1. INTRODUCTION

This SAP contains the definitions of analysis sets, derived variables, and statistical methods that will be used to evaluate the reactogenicity, safety and immunogenicity analysis of the VAC52416BAC3002 (E.ngage) study. The specifications of individual tables, listings and figures to be generated in each analysis will be described in the Data Presentation Specifications document.

This SAP is developed in line with the CSP Amendment 1 approved on 22 September 2023.

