5.6.1. Adverse Events

5.6.1.1. Definitions

Solicited AEs shown in the tables are extracted from the investigator assessment pages (Clinical Events) of the eCRF. All solicited AEs at the injection site (local) are considered related to the study vaccine administration.

For unsolicited AEs, only the AEs within the 29-day period following each vaccination will be presented in the safety tables except for MAAE and SAE which will be captured and tabulated in the outputs covering the whole study period.

The severity of the AEs will be classified as Grade 1 to 4. Solicited or unsolicited events that are graded less than Grade 1, are not considered as AE.

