5.6.2. Vital Signs

Vital signs (systolic and diastolic blood pressure [while sitting], heart rate, respiratory rate, and body temperature) will be measured both before vaccination and after the end of the 30-minute observation period. At non-vaccination visits, vital signs may be measured if deemed necessary by the investigator.

Baseline and emerging vital signs abnormalities after vaccination will be listed based on the abnormality gradings in [Appendix 4](#) (Section 6.4). An abnormality will be considered as emerging in a particular period if it is worse than the baseline value. If the baseline is missing, the abnormality is always considered emerging.

Any clinically significant changes in vital signs will be reported as an AE. Any clinically significant changes in vital signs that are observed prior to the first vaccination will be reported as medical history.

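### SAP Appendix 4 and protocol Appendix 5 grade systolic readings of 156 to 160 mm Hg differently, and the SAP's reason for merging Grades 3 and 4 does not hold for fever

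*SAP*

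**What the plan says.** **Protocol.** Section 10.3.3 makes Appendix 5 the severity scale for adverse events: "All AEs and laboratory data will be coded for severity using a modified version of the FDA grading table". In the vital-signs table of Appendix 5, systolic hypertension is 141-150 (Grade 1), 151-155 (Grade 2) and above 155 mm Hg (Grade 3). Only the Grade 4 cell of that row is marked as revised by the sponsor. Section 9.4.4 says that vital-sign abnormalities will be listed and that clinically significant changes are reported as adverse events. It names no scale for the listing.

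**SAP.** Section 1 states: "This SAP is developed in line with the CSP Amendment 1 approved on 22 September 2023". Section 5.6.2 supplies the scale for the listing: "Baseline and emerging vital signs abnormalities after vaccination will be listed based on the abnormality gradings in" Appendix 4. There, systolic hypertension is 141-150, 151-160 and above 160 mm Hg, and the last two cells are marked as revised by the sponsor. Below the table, the SAP says that "only values will be used to assign abnormalities, no clinical interpretations will be used", and continues: "Therefore, Grade 3 and 4 will be combined because Grade 4 always requires clinical interpretation". The fever row of the same table sets Grade 4 at above 40 °C / above 104.0 °F.

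**The concern.** Two severity scales apply to the same measurement in one trial. Sites grade a hypertension adverse event on protocol Appendix 5, while the sponsor's program grades the underlying reading on SAP Appendix 4. In a 5 mm Hg band the two give different grades, and the band lies at the Grade 2/3 boundary. That boundary matters because SAP 5.6.1.2 plans adverse-event tables for events of at least Grade 3.

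The Grade 3/4 merger is a separate matter of logic. The SAP decides to grade on values alone and then merges the top two grades on the ground that Grade 4 cannot be read from a value. For one row of its own table it can.

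At stake is whether the vital-sign listing can be read alongside the adverse-event tables without unexplained differences in grade.

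**Working it through.** No sample-size, power or alpha figure is involved. The check compares the two tables row by row and value by value.

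**1. Systolic row, side by side (mm Hg)**

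| Grade | Protocol Appendix 5 | SAP Appendix 4 |
|---|---|---|
| 1 | 141-150 | 141-150 |
| 2 | 151-155 | 151-160 (sponsor-revised) |
| 3 | >155 | >160 (sponsor-revised) |

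Grading every whole number from 90 to 220 mm Hg on both scales gives disagreement at exactly five values: 156, 157, 158, 159 and 160. Each is Grade 3 on the protocol scale and Grade 2 on the SAP scale. All other values agree.

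**2. Fever row.** The cells are the same in both documents: Grade 3 is 39.0-40.0 °C and Grade 4 is above 40 °C. Grading 36.0 to 42.0 °C in steps of 0.1, every reading from 40.1 °C upward is Grade 4 in both tables but falls into the combined Grade 3/4 category under the SAP rule.

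**3. Remaining five rows** (tachycardia, bradycardia, diastolic hypertension, systolic hypotension, respiratory rate). The cut-offs are the same in both documents. Grade 4 is hospitalization or intubation, so a value alone cannot reach it and the merger changes nothing. The mismatch therefore touches two of seven rows.

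**4. Where each scale is used**

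- SAP Appendix 4 feeds only the listing in SAP 5.6.2.
- Unsolicited adverse events carry the severity assigned under protocol 10.3.3. A vital-sign reading enters those tables only if it is a clinically significant change reported as an adverse event.
- Solicited fever does not pass through SAP Appendix 4: "Solicited AEs shown in the tables are extracted from the investigator assessment pages (Clinical Events) of the eCRF". Protocol 10.3.3 derives its severity from the temperature and has the investigator verify it on Appendix 5. SAP 5.6.1.2 tabulates solicited events by worst grade, so Grade 4 fever stays visible there.
- SAP 5.6.2 calls an abnormality emerging if it is worse than baseline. If that is programmed by grade, a rise from 152 to 158 mm Hg goes from Grade 2 to Grade 3 on the protocol scale but stays at Grade 2 on the SAP scale. The text does not say whether grade or value is compared.

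**5. How many readings lie in the band.** The documents give no blood-pressure distribution. As an assumption, take resting systolic pressure as normal with the means and SDs below. With Φ the standard normal distribution function:

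P(156-160) = Φ((160.5 − mean)/SD) − Φ((155.5 − mean)/SD)

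| Mean, SD | P(156-160) | Of 932 participants | Share of readings above 155 |
|---|---|---|---|
| 130, 16 | 2.7% | 25 | 49% |
| 135, 17 | 4.7% | 44 | 41% |
| 140, 18 | 6.7% | 63 | 35% |

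These are per scheduled measurement; four are scheduled (before and after vaccination on Days 1 and 30). They count readings that change grade, not adverse events that conflict with the listing.

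**The case against.** The case against acting is that this is a consistency point in a minor output, and much of that case stands.

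- **The listing has no prescribed scale.** Protocol 10.3.3 governs adverse events and laboratory data, and protocol 9.4.4 names no scale for the listing. The SAP may supply one. This stands: it is a mismatch between two tables, not a breach of a specified method.
- **The change looks deliberate.** Both altered SAP cells carry the sponsor-revision mark. This stands, but the protocol table has no matching revision, the SAP gives no reason, and the SAP says that it follows Amendment 1.
- **The output is descriptive.** No safety testing or formal group comparison is planned, and the same cut-offs apply to both groups. This stands.

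Four stronger readings are tempting, and the documents do not support them.

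- A reader might infer that the listing will contradict the adverse-event tables for every reading in the band. It can do so only where the investigator reports a clinically significant change as an adverse event.
- A reader might infer that Grade 4 fever is hidden in the trial. It is kept in the solicited-event tables. In the listing, a scheduled reading above 40 °C is also unlikely: temperatures are scheduled before vaccination and after the 30-minute observation, and protocol 5.5 treats fever in the preceding 24 hours as a temporary contraindication.
- A reader might infer that the merger lowers the count of severe abnormalities. It does not; the number at Grade 3 or above is unchanged.
- A reader might take the silence of the SAP version history as an unrecorded change. The history logs changes from version 1.0 to 2.0. If version 1.0 already had these cut-offs, there was nothing to log, and version 1.0 is not available here.

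None of this removes the two contradictions. One reading has two grades depending on the table used, and the stated reason for the merger is untrue for fever.

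**Conclusion.** The point holds, with limited reach. The two scales differ for systolic readings of 156 to 160 mm Hg and agree at every other systolic value. The reason given for merging Grades 3 and 4 is contradicted by the SAP's own fever row. The consequence is confined to the descriptive vital-sign listing and to possible disagreement between that listing and the adverse-event tables for the same measurement. No immunogenicity result and no solicited-event table is affected.

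The table comparison needs no assumption. The 2.7% to 6.7% of readings in the band rests entirely on the assumed distributions and should not be quoted as a number of conflicting events. Which systolic cut-off is clinically right is not judged here; the passages must be reconciled.

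**What to change.** 1. Reconcile the systolic rows of protocol Appendix 5 and SAP Appendix 4, so that one set of cut-offs serves both adverse-event grading and the listing, and document which set is intended. If it is the protocol's, change two cells in the SAP. If it is the sponsor-revised set, amend the protocol table and give the reason in the SAP.
2. Rewrite the last sentence of SAP Appendix 4 so that Grades 3 and 4 are combined only in rows where Grade 4 is not numeric, and list fever above 40 °C as Grade 4.

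Cost on the SAP side: two table cells, one sentence and minor programming, with no new data. The alternative for item 1 costs a protocol table amendment.
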